#### A-4. Trials on the Effects of Sodium Supplementation on Blood Pressure in Persons with Diabetes

Study	Design	Comparison	N	Age (yrs)	Males (%)	Race	Population	Study Dur (wks)	BP Δ in intervention group	BP Δ in control group	Between-group Difference in BP Δ	Contrast in urine sodium
Mulhauser, 1996	Parallel study	Sodium supplement vs. placebo	14	31	75	NR	Type 1 diabetes, on insulin, increased proteinuria, high normal or mildly hypertensive BP	4	Systolic mean diff, 3.2 (-2.6 to 9) Diastolic mean diff, 2.2 (-1.8 to 6.2)	Systolic mean diff, -1.7 (-8.6 to 5.3) Diastolic mean diff, -3.1 (-5.9 to -0.4)	Systolic: 4.9 (-3.3 to 13.1) NS Diastolic: 5.3 (1 to 9.7) p=0.02	Urinary Na excretion (mmol/day): Placebo, 92±33 Supplement, 199±52 p=0.0002 compared to placebo
Suckling, 2016	Crossover study	Reduced salt (90mmol) vs. placebo	26	56	54	White: 65 Black: 23 Asian: 12	Diet-controlled type 2 diabetes or IGT, untreated normal or high normal BP	12			BP fell from 135.5±2.0/81.3±1.1 mmHg with salt to 131.2±1.9/79.7±1.2 mm Hg with placebo, that is, a fall of 4.2 mmHg in SBP (P<0.01) and fall in DBP of 1.7 mmHg (p=0.055)	During randomized crossover phase, mean 24-hour UNa was 165.1±9.0 mmol/24 hours (9.7g salt) on salt and 116.6±9.5 mmol/24 hours (6.8g salt) on placebo. The reduction in salt intake was, therefore, 48.6±9.3 mmol (2.9g salt) from salt to placebo. UNa excretion was lower in placebo vs. salt group (p<0.001)

# Appendix B: Continuous Glucose Monitoring (CGM) Ancillary Study

## 1. Ancillary Study Details

**Official Project Title:** Effects of the DASH diet on glucose patterns in adults with type 2 diabetes

**Principal Investigator:** [name], MPH  
Johns Hopkins Bloomberg School of Public Health

**Funded By:** National Institute of Diabetes and Digestive and Kidney Diseases (NIDDK)

**Grant #:** R01DK128900

## 2. Rationale

The overarching goal is to evaluate how the DASH4D dietary pattern modifies glucose patterns in adults with type 2 diabetes. This ancillary study to the DASH4D protocol will add continuous glucose monitoring (CGM) combined with symptom reporting in all participants in the DASH4D trial (N=100) during screening (between SV2 and the start of the run-in) and during the two weeks at the end of each of four feeding periods. This ancillary study also includes laboratory testing for diabetes and cardiac biomarkers of biospecimens collected as part of the main DASH4D trial. This study will answer the question: Does the DASH4D diet (a DASH-style diet modified for people with diabetes) improve glucose control and reduce glycemic variability in adults with type 2 diabetes?

## 3. Background

Dietary guidelines for persons with diabetes are largely directed at reducing hyperglycemia. The DASH diet is rich in fruits, vegetables, and low-fat dairy products with reduced saturated fat and cholesterol. The DASH eating plan is recommended by the ADA for adults with diabetes based on evidence that it helps control blood pressure and lowers cardiovascular risk in the general population. The direct effects of the DASH diet on glucose control and glycemic excursions are uncharacterized. The DASH4D trial provides an opportunity to evaluate how diet may affect hyperglycemia and glucose patterns using CGM. Glucose patterns in adults with type 2 diabetes are relatively uncharacterized, and no prior study has examined the effect of diet on CGM parameters in a controlled feeding study. The addition of the symptom reporting survey during CGM wear will allow us to understand how certain symptoms relate to changes in glucose levels.

## 4. Study design

[figure not shown]
We propose to add 14-day CGM assessment in participants in the DASH4D trial (N=100) during screening (up to 14 days, or the start of Run-In, whichever comes first) and each of the four feeding periods, for a total of five 14-day CGM periods (see green lines in **Figure CGM-1**).

As part of the main trial, each participant will complete screening, a run-in period, and four feeding periods lasting 5 weeks each, separated by at least 1 week of a break (eating own food).

During the screening phase and at randomization, DASH4D screenees will be invited to participate in, and consent for, this ancillary study, which is optional. CGM sensors will be placed during week 3 of each feeding period (typically on Thursday, which is the last day of in-person feeding every week). Sensors will be worn up to 14 days. Thus, CGM data collection will typically begin during week 3 and end during week 5 for every feeding period.

During each period of CGM device wear, we will also ask participants to complete a symptom reporting survey at least daily to indicate whether they experienced any symptoms that may relate to changes in their glucose levels, along with reporting the time of symptom onset.

**Figure CGM-1. Design of the DASH4D CGM Study.**

## 5. Exclusions

Participants will be excluded from participating in the CGM ancillary study if they have a history of allergic skin reaction to adhesive or an implantable medical device, such as a pacemaker. Participants who do not wish to participate in the CGM ancillary study will still be allowed to participate in the DASH4D trial.

## 6. Procedures

We will use the FreeStyle Libre Pro CGM device (Abbott; <https://provider.myfreestyle.com/freestyle-libre-pro-product.html>) to measure glucose in up to five 14-day periods (during screening, CGM wear may be <14 days) in all participants who consent to this protocol (**Figure CGM-2**). The version of the device used in this ancillary study does not reveal the glucose readings to participants, which will be provided to participants after the data collection phase of the trial ends (see section 9 Reporting below).

**Figure CGM-2. FreeStyle Libre Pro CGM System.**

The FreeStyle Libre Pro system is FDA approved for use in continuous monitoring of glucose in persons with diabetes who are aged 18 or older. The system is designed for professional use to reveal glucose trends and patterns, which are downloaded from the sensor using a reader following up to 14 days of wear. The sensor is held in place with an adhesive and has two main parts: 1) a transmitter patch, which is about the diameter of a quarter and thickness of two quarters that collects and stores data on glucose, and 2) a flexible very thin filament (<4mm) sensor inserted just under the skin to measure interstitial glucose. The application of the sensor is painless and most patients report that they cannot feel the sensor when it is being worn.

After obtaining informed consent as part of the main screening and trial consents, trained study staff will place the sensor on the back of the upper arm using a disposable applicator at SV1 and during the third week of each of the four feeding periods. The sensor will be covered with an adhesive bandage designed for use with the Libre sensor to prevent accidental dislodgement. At least 2 minutes after placement, staff will check the status of each sensor to ensure it is working properly.

The sensor is worn on the arm for 14 days (may be shorter during screening) and is factory calibrated (no fingerstick is required). The Libre Pro system records interstitial glucose every 15 minutes and stores the 14 days of data. DASH4D participants will be provided with instructions for wear of the device. The device stays on for each 14-day period and can be worn while showering, swimming, or exercising. Staff will be available (in-person and by phone) to answer any questions and will encourage participants to wear the device for the full 14-day period. After day 14 of each wear period, staff will remove the device during the next pre-scheduled trial visits. The Libre Pro sensors require a hand-held reader to download information on glucose values. After removal, sensors will be labeled, and the data will be downloaded by staff using the Libre Pro Reader (**Figure CGM-3**).

**Figure CGM-3. Libre Pro Reader.**

## **7. Symptom Reporting Survey**

During each period of CGM device wear, participants will be asked to complete a symptom reporting survey to report each time they experience one of the listed symptoms, along with the time of symptom onset, or to report that none of the symptoms of interest occurred that day. Participants will ideally complete the symptom reporting via REDCap survey links that will be sent via text message, so that they can better report symptoms in real-time or near real-time. However, participants may elect to complete the symptom reporting as a paper-based diary if they do not wish to receive text messages or complete a mobile survey.

## **8. Safety/Risks**

There is minimal risk or discomfort associated with use of the CGM sensor. The main risk is skin irritation from the adhesive. There is a very small risk of developing a local skin infection at the site of the sensor filament placement. The risk will be mitigated by using sterile technique during placement. The Libre Pro system does not have alarms and does not provide any real-time information to the participant. Throughout the trial, participants will continue routine glucose monitoring as recommended by their doctor. Participants will be counseled not to ignore symptoms that may be due to low or high blood glucose, or dehydration. The CGM device is contraindicated for wear during MRI, CT scan, X-ray, or diathermy treatment. During any medical treatment, participants should inform their health care provider that they are wearing a CGM sensor. The sensor should be removed before any MRI, CT scan, X-ray, or diathermy treatment. Confidentiality will be maintained by labeling the used sensors with a coded number and following data security procedures already in place as part of the DASH4D trial.

## **9. Reporting**

Participants will not be aware of their glucose measures collected during the 14-day wear periods. A report with a summary of the 14-day glucose data from the screening phase (mean glucose, standard deviation, and a graph of glucose values with information on the normal range)

will be provided back to participants after they complete the feeding phase of the trial or are closed out of screening (i.e., not randomized). CGM technology is often used in the care of adults with type 1 diabetes. It is not standard of care for adults with type 2 diabetes, and it is not commonly used in this population. Even if subsequent analysis of the CGM data reveals clinically relevant glucose patterns, this information is not directly clinically actionable at a later date, especially in the absence of insulin therapy.

## 10. Study Outcomes and Objectives

Based on prior studies, we hypothesized that salt would have no effect on glucose. Therefore, we plan to combine data from the lower and higher sodium feeding periods for each diet to increase statistical power (i.e., combine data collected during the DASH4D lower sodium diet with data collected during the DASH4D higher sodium diet). Our primary aim is to examine the effects of the DASH4D diet (vs. comparison diet) on glucose control and glycemic variability in adults with type 2 diabetes.

Primary, secondary, and exploratory CGM outcomes were selected based on clinical guidelines and recommendations from a consensus statement on CGM endpoints for clinical trials. CGM outcomes will be based on CGM data captured by sensors worn from week 3 to week 5 (up to 14 days) of each 5-week feeding period in participants included in the DASH4D-CGM ancillary study. Per current analytic recommendations, CGM outcomes will be generated using all available CGM data for each feeding period.

### 10.1 Primary CGM outcomes

10.1.1 **CGM mean glucose (mg/dL):** The mean of glucose measurements collected during the 14-day wear period will be used as a primary outcome of the corresponding feeding period.

10.1.2 **Percentage of time between 70 and 180 mg/dL:** The percentage of time glucose was between 70 and 180 mg/dL (time-in-range) during the 14-day wear period will be used as a primary outcome of the corresponding feeding period.

10.1.3 **Coefficient of variation (%):** The coefficient of variation (standard deviation divided by mean glucose, multiplied by 100) of glucose measurements collected during the 14-day wear period will be used as a primary outcome of the corresponding feeding period.

### 10.2 Secondary CGM outcomes

10.2.1 **Glucose standard deviation (mg/dL):** The standard deviation of glucose measurements will be used as a secondary outcome of the corresponding feeding period.

10.2.2 **Percentage of time above 180 mg/dL:** The percentage of time glucose was above 180 mg/dL will be used as a secondary outcome of the corresponding feeding period.

10.2.3 **Percentage of time above 250 mg/dL:** The percentage of time glucose was above 250 mg/dL will be used as a secondary outcome of the corresponding feeding period.

10.2.4 **Percentage of time below 70 mg/dL:** The percentage of time glucose was below 70 mg/dL will be used as a secondary outcome of the corresponding feeding period.

10.2.5 **Percentage of time below 54 mg/dL:** The percentage of time glucose was below 54 mg/dL will be used as a secondary outcome of the corresponding feeding period.

### ***10.3 Exploratory CGM outcomes***

10.3.1 **Percentage of time between 70 and 140 mg/dL:** The percentage of time glucose was between 70 and 140 mg/dL will be used as an exploratory outcome of the corresponding feeding period.

10.3.2 **Percentage of time above 140 mg/dL:** The percentage of time glucose was above 140 mg/dL will be used as an exploratory outcome of the corresponding feeding period.

10.3.3 **Proportion of participants with >70% time between 70 to 180 mg/dL:** The proportion of participants that spent >70% of time with glucose between 70 and 180 mg/dL will be used as an exploratory outcome of the corresponding feeding period.

10.3.4 **Proportion of participants with coefficient of variation <36%:** The proportion of participants with coefficient of variation <36% will be used as an exploratory outcome of the corresponding feeding period.

10.3.5 **Proportion of participants with <25% time above 180 mg/dL:** The proportion of participants that spent <25% of time with glucose above 180 mg/dL will be used as an exploratory outcome of the corresponding feeding period.

10.3.6 **Proportion of participants with <5% time above 250 mg/dL:** The proportion of participants that spent <5% of time with glucose above 250 mg/dL will be used as an exploratory outcome of the corresponding feeding period.

10.3.7 **Proportion of participants with <4% time below 70 mg/dL:** The proportion of participants that spent <4% of time with glucose below 70 mg/dL will be used as an exploratory outcome of the corresponding feeding period.

10.3.8 **Proportion of participants with <1% time below 54 mg/dL:** The proportion of participants that spent <1% of time with glucose below 54 mg/dL will be used as an exploratory outcome of the corresponding feeding period.

## 10.4 Primary aim

Examine the mean differences in mean glucose, time-in-range, and glucose coefficient of variation on the DASH4D diet compared to the comparison diet, in a combined analysis across both levels of sodium.

- We hypothesize that the DASH4D diet will result in improved glucose control (lower mean glucose, higher time-in-range) and glycemic variability (lower glucose coefficient of variation) compared to the comparison diet.

## 10.5 Secondary aims

10.5.1 Examine the mean differences in glucose standard deviation and time spent with hyperglycemia and hypoglycemia on the DASH4D diet compared to the comparison diet, in combined analyses across both levels of sodium.

10.5.2 Examine the mean differences in exploratory outcomes (described in 10.3) on the DASH4D diet compared to the comparison diet, in combined analyses across both levels of sodium.

# 11. Statistical Analysis

## 11.1 Analytic population

Among all randomized participants, those who completed CGM during one or more feeding period will be included in the analyses.

## 11.2 Statistical analyses

All primary analyses are summarized in **Table CGM-1**. We will conduct all primary analyses using an intention-to-treat approach. We will use linear (for continuous outcomes) or logistic (for binary outcomes) mixed effect models and compare differences in CGM outcomes while consuming the DASH4D (versus comparison) diet.

Our primary contrast will be between the DASH4D and comparison diet (combining across both levels of sodium) on mean glucose, time-in-range, and coefficient of variation (**Primary Aim – 10.4**). Secondary contrasts will assess the effects of the DASH4D (versus comparison) diet on glucose standard deviation, time spent with hyperglycemia, and time spent with hypoglycemia (**Secondary Aim – 10.5.1**) and on exploratory outcomes (**Secondary Aim – 10.5.2**). Because CGM outcomes are not independent, we will not make adjustments for multiple comparisons.

We will conduct several sensitivity analyses. First, to test our assumption that sodium does not affect glucose, we will assess the effects of the higher (versus lower) sodium diet on all primary CGM outcomes, stratified by different diets (**Sensitivity analysis 1a**). We will also examine whether the effects of the DASH4D diet on all CGM outcomes are modified by sodium levels by exploring diet-sodium interactions (**Sensitivity analysis 1b**). Second, we will re-estimate all analyses using a per-protocol approach (**Sensitivity analysis 2**). For these analyses, participants without perfect adherence on >90% of days for a given diet will be excluded. Perfect adherence

was defined as eating all provided study foods and not eating any non-allowed foods or beverages.

For each feeding period, we will only include data from participants who wore CGM sensors for 10 or more days (**Sensitivity analysis 3**). Current guidelines suggest that sensors may need to be worn  $\geq 70\%$  of the time (~10 out of 14 days for the Abbott Libre Pro) to accurately represent glycemic control.

### 11.3 Exploratory analyses

We will conduct two sets of exploratory analyses. First, we will estimate the linear mixed models to examine the effect the DASH4D (versus comparison) diet on the main CGM outcomes, stratified by age (<65, 65+), sex (male, female), baseline HbA1c (<7%, 7-7.9%, 8-8.9%), number of glucose-lowering medications used (0, 1, 2+), and type of diabetes medications used (no medication used, non-insulin or sulfonylureas, insulin or sulfonylurea). The DASH4D-CGM study is not powered to detect differences across any specific subgroup. Therefore, these analyses are exploratory and will not be adjusted for multiple comparisons.

Second, we will visually compare average hourly and daily mean glucose, time-in-range, and coefficient of variation across the DASH4D (versus comparison) diet. These analyses are exploratory and designed to examine how long participants may need to consume the DASH4D diet before an effect is evident and whether diet effects vary across daytime versus nighttime. Daily averages will be calculated using each 24-hour of CGM data. These analyses are similar to results reported in other major CGM trials.

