#### **4.7 Subgroup analysis**

Protocol pre-specified subgroup analyses will be conducted using mixed-effects linear models or the GEE approach, consistent with the analyses proposed for each outcome as described previously. Pre-specified subgroups of interest are those defined by gender (women, men), race (Black, non-Black), baseline level of the outcome of interest, baseline number of medications used to treat the outcome, and chronic kidney disease status. The mean models for the analysis will be augmented with binary subgroup indicator(s) and appropriate cross-product interaction terms of subgroup indicator(s) by diet indicators. The differential intervention effects between subgroups will be evaluated through estimating the regression beta coefficient of the interaction terms and the corresponding 95% CIs. Subgroups with less than 10 participants will not be reported. The trial is not powered based on any specific subgroup analyses so these analyses are exploratory and will not be adjusted for multiple comparisons.

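### The exploratory CGM subgroup analyses give diet effects by stratum but specify no diet-by-subgroup interaction estimate, and the HbA1c strata leave out an eligible value

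*Combined protocol and SAP*

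**What the plan says.** Appendix B 11.3 plans the subgroup work in one sentence: "we will estimate the linear mixed models to examine the effect the DASH4D (versus comparison) diet on the main CGM outcomes, stratified by age" and four further factors. Age and sex have two levels each. The next two factors are given as "baseline HbA1c (<7%, 7-7.9%, 8-8.9%), number of glucose-lowering medications used (0, 1, 2" or more), and medication type also has three levels. The section adds that "The DASH4D-CGM study is not powered to detect differences across any specific subgroup" and that "these analyses are exploratory and will not be adjusted for multiple comparisons". It names no diet-by-subgroup term, heterogeneity test or rule for comparing strata.

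Two other places handle the same kind of question differently:

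- **Appendix B 11.2, for sodium.** Sensitivity analysis 1a is a stratified analysis: "we will assess the effects of the higher (versus lower) sodium diet on all primary CGM outcomes, stratified by different diets". Sensitivity analysis 1b then asks whether the diet effects "are modified by sodium levels by exploring diet-sodium interactions". Table CGM-1 marks only 1b as an interaction.
- **SAP 4.7, for the main trial.** Subgroup indicators and their products with the diet indicators enter the model, and "The differential intervention effects between subgroups will be evaluated through estimating the regression beta coefficient of the interaction terms", with 95% CIs.

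**The concern.** A subgroup analysis is normally read as asking whether the effect differs between groups. Estimates within strata do not answer that directly. One stratum can have a confidence interval that excludes zero and another an interval that includes it while the true effect is the same in both. The quantity that addresses effect modification is the difference between strata, with its own uncertainty. Appendix B 11.3 mentions such differences only to say that the study is not powered for them, and plans no estimate of them.

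What is at stake is the interpretation of secondary material. Anyone asking whether the diet works differently by, say, medication use would have only a list of stratum results to go on.

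**Working it through.** **Inputs from the documents.** There are five factors with 2 + 2 + 3 + 3 + 3 = 13 strata (Appendix B 11.3) and three primary CGM outcomes (Appendix B 10.1). CGM participation is optional within N=100 (Appendix B 4).

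**Assumptions.** The main CGM outcomes are taken to be the three primary ones. Alpha is 0.05 two-sided, as in SAP 4.2.1; Appendix B states none. The true diet effect is the same in every stratum, and strata are of equal size. Overall CGM power is varied, because Appendix B gives no power, effect size or SD. There is no CGM figure in the plan to reproduce.

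**Number of estimates.** 13 strata x 3 outcomes = 39 stratum estimates.

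**Chance disagreement on significance.** With k equal strata, stratum power is p = Phi((1.96 + z_power)/sqrt(k) - 1.96). The probability that at least one stratum is significant and at least one is not is 1 - p^k - (1 - p)^k. With no diet effect, p = 0.05.

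Example at 80% overall power, k = 2: p = Phi(2.80/1.414 - 1.96) = Phi(0.02) = 0.51, so disagreement is 1 - 0.51^2 - 0.49^2 = 0.50.

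| Overall power | p, 2 strata | Disagree, 2 strata | p, 3 strata | Disagree, 3 strata |
|---|---|---|---|---|
| No effect | 0.05 | 9.5% | 0.05 | 14% |
| 50% | 0.28 | 41% | 0.20 | 49% |
| 80% | 0.51 | 50% | 0.37 | 70% |
| 90% | 0.63 | 47% | 0.46 | 75% |
| 95% | 0.72 | 40% | 0.55 | 74% |
| 99% | 0.86 | 24% | 0.70 | 63% |
| 99.9% | 0.95 | 10% | 0.83 | 42% |

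The spans are about 10-50% for two strata and 14-75% for three. For equal strata, 50% and 75% are the maxima, reached at p = 0.5. Unequal strata can go slightly higher: a 30:70 split gives 55% at 80% overall power.

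**What an interaction test offers.** Its nominal false-positive rate is 5% per test. There would be 5 factors x 3 outcomes = 15 tests; if they were independent, the chance of at least one false positive would be 1 - 0.95^15 = 54%. Power is low. In a 50:50 subgroup the interaction has twice the standard error of the overall effect. An interaction as large as the overall effect is therefore detected with probability Phi(2.80/2 - 1.96) = 29% if overall power is 80%, and Phi(3.24/2 - 1.96) = 37% if it is 90%.

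**HbA1c strata.** Protocol Table 1 excludes HbA1c above 9.0%, so 9.0% is eligible. The top stratum in Appendix B 11.3 ends at 8.9%, so that value has no stratum. Eligibility rests on the point-of-care test at the first screening visit (protocol 8.2). If baseline HbA1c is instead taken from the stored third-visit specimen, values above 9.0% could also fall outside.

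**The case against.** The strongest reply is that the plan claims very little. The analyses are called exploratory and unpowered, multiplicity is openly left unadjusted, and nothing says that significance will be compared across strata or effect modification declared. This stands and keeps the point minor. It does not supply an estimate of the difference, and a wide interaction interval would show the lack of power more plainly than a caveat does.

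A reader might infer that a separate model is fitted in each stratum, with variance components re-estimated in small groups. The text does not establish that. SAP 4.1 also calls the sodium effects stratified by diet, and SAP 4.3 takes them as contrasts from one joint model. Nor does Appendix B 11.3 rule out an interaction term. What can be said is that none is specified.

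It could also be argued that the closing sentence of SAP 4.6, which extends similar strategies to outcomes outside the aims, covers this. It does not name CGM outcomes, Appendix B has its own analysis section, and that section does not refer to SAP 4.7.

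Finally, the remedy has limits: 15 unadjusted interaction tests can produce chance findings, and their power is low. That is true, but each would at least address the question of effect modification.

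**Conclusion.** The omission is real and small. Appendix B 11.3 provides stratum estimates without an estimate of whether the diet effect differs, while the same document uses an interaction for main-trial subgroups and for sodium. The HbA1c gap at 9.0% is a separate, certain inconsistency with the eligibility criteria.

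The size of the interpretive risk cannot be fixed from the documents. The 10-50% and 14-75% ranges rest on assumed power, equal strata and a uniform effect. Quoting only the values at 80-90% power (47-50% and 70-75%) would be selective. A reader might also infer that false subgroup claims are therefore likely. The documents do not support that, because disagreement on significance becomes a claim only if someone interprets it as one. The primary and secondary CGM analyses are unaffected.

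**What to change.** In Appendix B 11.3, for each of the five factors, specify one mixed model with a diet-by-subgroup interaction, as in SAP 4.7. Report the interaction estimate with its 95% CI as the evidence on effect modification; three-level factors need two contrasts and a joint test. Keep the stratum estimates as descriptive.

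Change the top HbA1c stratum to 8% or higher, and state which measurement defines baseline HbA1c.

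The cost is a few lines of wording and one interaction per model, with no new data. The price in interpretation is up to 15 low-power interaction assessments without multiplicity control, which should stay labelled exploratory. Entering age and HbA1c as continuous terms is optional: it goes beyond SAP 4.7, which uses subgroup indicators, and adds a linearity assumption.

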4 STATISTICAL ANALYSIS FRAMEWORK

4.1 Overview

This trial is a randomized, four-period crossover study that tests the effects of 4 diets (specified by the combinations of 2 diet factors – DASH4D vs Comparison and 2 sodium levels – Higher vs Lower) on a specified set of outcomes. The 4 diets are denoted DH (DASH4D-Higher sodium), CH (Comparison-Higher sodium), DL (DASH4D-Lower sodium), and CL (Comparison-Lower sodium). Each participant receives all 4 diets. Each diet is eaten for 5 consecutive weeks. The order in which participants eat these diets is random. A break of at least 1 week (typically 2 weeks), where participants are eating their own food, will separate each consecutive set of feeding periods.

		DIETARY PATTERN	
		Comparison	DASH4D
SODIUM LEVEL	Higher (3700mg)	CH (ref*)	DH
	Lower (1500 mg)	CL	DL

\*reference group for the primary contrast

The primary outcome of the trial is end-of-period systolic BP (SBP), with the primary contrast testing the mean SBP difference between the DL and the CH diets (Primary Aim). The secondary contrasts focus on the effects of sodium on SBP stratified by diet types (DH vs DL and CH vs CL, Secondary Aim 1.2.1), and the effect of diet on SBP stratified by sodium levels (DH vs CH and DL vs CL, Secondary Aim 1.2.2). The trial will examine whether the diet and sodium effects are additive through exploring for diet-sodium interaction on SBP (Secondary Aim 1.2.3), and assess the time course of the sodium effects on SBP by diet types (Secondary Aim 1.2.4) and the diet effects on the time course of SBP by sodium levels (Secondary Aim 1.2.5) over the 5-week feeding period. We will also assess the effects of these diet contrasts on other protocol-specified outcomes, namely, diastolic BP (DBP; Secondary Aim 1.2.6), fasting glucose, fructosamine, plasma lipids, CVD risk scores, patient-reported outcomes, and specified safety outcomes, SAEs and adverse medical events (Secondary Aim 1.2.7). We will assess the differences of the aforementioned outcomes under the specified diet contrasts by pre-specified subgroups (Secondary Aim 1.2.8).

Aim	Outcome	Timing	Contrast
Primary 1.1	SBP	End of Period	CH vs DL
Secondary 1.2.1	SBP	End of Period	DH vs DL; CH vs CL
Secondary 1.2.2	SBP	End of Period	DH vs CH; DL vs CL
Secondary 1.2.3	SBP	End of Period	(DH-DL) vs (CH-CL)*
Secondary 1.2.4	SBP	Period Trajectory	DH vs DL; CH vs CL
Secondary 1.2.5	SBP	Period Trajectory	DH vs CH; DL vs CL

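### The CGM plan asks whether the diet effect differs between day and night but plans only a visual comparison, although the crossover data allow a within-person estimate with an interval

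*Combined protocol and SAP*

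**What the plan says.** Appendix B section 11.3 describes two exploratory sets. The first fits linear mixed models within subgroups. For the second, "we will visually compare average hourly and daily mean glucose, time-in-range, and coefficient of variation across the DASH4D (versus comparison) diet". Its status and first purpose follow: "These analyses are exploratory and designed to examine how long participants may need to consume the DASH4D diet before an effect is evident". A second purpose, the one at issue here, is to learn "whether diet effects vary across daytime versus nighttime". The section adds that this resembles reporting in other large CGM trials.

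Nothing else in Appendix B serves the day-night question. The outcomes in 10.1 to 10.3 include no day or night measure. Table CGM-1 has no such row. No clock hours are given.

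The rest of the CGM plan is model-based. Section 11.2 says "We will use linear (for continuous outcomes) or logistic (for binary outcomes) mixed effect models", and sensitivity analysis 1b asks whether the diet effect is "modified by sodium levels by exploring diet-sodium interactions". On the data, Appendix B section 6 says "The Libre Pro system records interstitial glucose every 15 minutes and stores the 14 days of data", and SAP section 4.1 says "Each participant receives all 4 diets".

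**The concern.** Whether a diet effect differs by time of day is a difference of differences: the diet effect by day minus the diet effect by night. Looking at averages gives a rough impression of that quantity but no statement of its uncertainty. With 24 clock hours and three metrics there are 24 × 3 = 72 hourly gaps to look at, and no rule for separating a pattern from noise. Because the windows are undefined, they could also be drawn after the plots have been seen.

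At stake is a secondary message in a CGM report. A sentence saying that the diet acts mainly by day, or equally round the clock, would have no planned interval behind it, although the trial collects what is needed to supply one.

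**Working it through.** The documents state no SD, power or precision for any CGM outcome, so there is no figure of the plan's to reproduce. Three things can be checked.

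**1. Do the data support a within-person contrast?**
- Readings per day at one per 15 minutes: 24 × 60 / 15 = 96.
- Readings per full wear: 14 × 96 = 1,344, or 4 × 14 = 56 per clock hour.
- With an assumed split of 16 h day and 8 h night: 14 × 64 = 896 day and 14 × 32 = 448 night readings per period.

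A participant with at least one period on each diet therefore supplies a day-minus-night difference under both. For someone with all four periods, the contrast is

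D = mean of (day − night) over the two DASH4D periods − mean of (day − night) over the two comparison periods.

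This equals the diet effect by day minus the diet effect by night.

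**2. How precise would it be?** The 95% CI half-width is t(0.975, n−1) × SD_D / √n. SD_D is not in the documents; I assume 10 to 40 mg/dL. Appendix B gives N=100, but CGM is optional, so smaller numbers are shown too.

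| N | SD_D 10 | 20 | 30 | 40 |
|---|---|---|---|---|
| 100 | 2.0 | 4.0 | 6.0 | 7.9 |
| 90 | 2.1 | 4.2 | 6.3 | 8.4 |
| 80 | 2.2 | 4.5 | 6.7 | 8.9 |

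(mg/dL, mean glucose)

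**3. Would intervals around each diet's own average serve instead?** I used a simulation of 4,000 replicates with these assumed SDs in mg/dL: between-person level 30, day-night difference 15, period-level error 12 per window, and person-to-person variation in the diet-by-window effect 10. These imply SD_D = √(12² + 12² + 10²) = 19.7, inside the range above.

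| N | Half-width, day-night contrast | Half-width, one diet's daytime mean |
|---|---|---|
| 100 | 3.9 | 6.4 |
| 90 | 4.1 | 6.8 |
| 80 | 4.4 | 7.2 |

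Coverage for the contrast was 95.3% to 95.8%. The hand formula agrees. For the contrast at N=100, 1.984 × 19.7 / 10 = 3.9. For one diet's daytime mean the variance is 30² + 7.5² + 12²/2 + 5² = 1,053, so the SD is 32.5 and the half-width is 1.984 × 32.5 / 10 = 6.4.

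The interval around a single diet's average includes between-person spread, which cancels in the contrast. Such intervals on the plots would not show the precision of the quantity in question.

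**The case against.** The best defence is that the analysis is openly exploratory, feeds no stated aim and follows an established style of CGM reporting. No section plans a claim that the diet works mainly by day. The hourly means by diet are point estimates, so what is missing is an interval rather than any estimate at all. All of this stands, and it limits the importance of the point. It does not explain the gap, because exploratory questions elsewhere in the same document are quantified. The first set in 11.3 is modelled. SAP 4.4 attaches a 95% CI to an exploratory interaction and uses loess plots to guide a model with confidence bands. SAP 4.7 gives interaction terms with 95% CIs for exploratory subgroups. The SAP does not formally govern Appendix B, but it shows the trial's usual practice.

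A reader might go further and infer that the gap between two plotted diet averages is far noisier than the within-person difference. The design does not support that. Assume n=90, SD 35 mg/dL for a period mean in one window, within-person correlation r=0.8 and two periods per diet. Each diet's mean then has SE 35 × √((1+0.8)/2/90) = 3.5. Treating the two diets as independent groups would give 3.5 × √2 = 4.95. They are the same people, however, so with complete data the plotted gap is the mean within-person difference, with SE 35 × √((1−0.8)/90) = 1.65 (2.02 at r=0.7, 1.17 at r=0.9). With r=0.8, SDs of 20 to 50 and n of 60 to 90 move it between about 0.9 and 2.9. The plotted gap already has the paired precision; what the plan lacks is a way to show it. These SEs also concern the diet effect within one window, not the day-night interaction.

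Complete data is a real condition. Section 11.1 admits anyone with CGM in one or more periods, so the plotted averages may come from partly different people.

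**Conclusion.** The point holds as a minor gap in method. Appendix B 11.3 poses an interaction question and plans only a visual answer, while the design and the models already in 11.2 can supply an estimate with an interval. The expected 95% CI half-width is about 2 to 8 mg/dL at N=100, and up to about 9 at N=80. This rests wholly on an assumed contrast SD of 10 to 40 mg/dL and on participants having CGM data on both diets.

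It should not be read as an error in the CGM study's main inference. The primary and secondary contrasts are modelled, and none depends on the hourly plots.

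**What to change.** In Appendix B 11.3:

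1. State the day and night clock hours before any unblinded analysis by time of day.
2. Derive mean glucose and time-in-range for each window in each feeding period.
3. Fit the linear mixed model with period, diet, window and diet-by-window. Section 11.2 does not list random effects, so write them down: participant and participant-by-period, because two windows from one period are correlated. A participant-by-window term makes this match the simpler alternative, which is to analyse each period's day-minus-night difference by diet and period with a participant effect.
4. Report the diet effect by day, by night and their difference with 95% CIs, labelled exploratory and without multiplicity adjustment, as elsewhere in 11.3.
5. Keep the hourly plots, since two fixed windows may miss a pattern at other hours, but add the within-person DASH4D-minus-comparison difference with its interval.

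The cost is a wording change and one more exploratory model on data already planned. No aim, outcome or sample size changes.
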